2.1.1.2 Data documented at unscheduled visits

Data collected at unscheduled visits will only be listed in by patient listings. In the summary tables, each parameter will only be tabulated for the visits at which it is scheduled.

[&]amp; For parameters of the 48-hour MBS Study for which separate measurements are available for the first and second 24-hour period, these values will be averaged to obtain a single per day value for this analysis visit. In case one of these measurements is missing, please refer to Section 2.2.1 for calculation of the per day value.

2.1.2 Calculation of Changes

2.1.2.1 Change from baseline

The absolute change from baseline (V1) to any visit during the treatment phase or to the follow-up (FU) visit will be calculated as the value at the visit minus the baseline value. If any of the two values is missing, the absolute change from baseline will be missing.

The relative change (fold increase) [%] is calculated by dividing the absolute change by the baseline value and by multiplying this ratio by 100 to obtain a percentage. If the absolute change is missing or if the baseline value is zero, the fold increase from baseline will be missing.

Concerning efficacy parameters of the 48-hour metabolic balance studies (MBS, see Section 2.2.1) for which separate measurements are available for the first and second 24-hour period, absolute changes from baseline to Week 24 (V9) are calculated as average of the measures obtained during the first 24-hour period (documented in the eCRF at Day 2) and during the second 24-hour period (documented in the eCRF at Day 3) of the MBS at V9 minus the average of the measures obtained during the first and second 24-hour period of the MBS at V1 (see calculation formula in Section 2.2.1). Dealing with missing measurements for one of the 24-hour periods at V1 (or V9, respectively) is described in Section 2.2.1. If any of the two averaged values is missing, the absolute change from baseline to Week 24 (V9) will be missing.

The baseline value will be the value tabulated for the 'Baseline' visit as described in Section 2.1.1.

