• Vital signs (body temperature, systolic/diastolic blood pressure, pulse rate) and body weight

For vital signs and body weight, standard descriptive summary statistics will be calculated for values at visits and for absolute changes from baseline.

Physical Examination

This will be summarized by the number and percentage of patients with normal/abnormal findings per body system at each visit.

• Electrocardiograms (ECG)

For the ECG parameters (heart rate, PR, QRS, QT, QTcF, RR), standard descriptive summary statistics will be calculated for values at visits and for absolute changes from baseline. Additional ECGs performed for cause as needed to evaluate AEs will only be listed.

• Laboratory parameters (hematology, biochemistry and urinalysis)

Values and absolute changes from baseline to post-baseline visits with an assessment of the respective clinical laboratory parameter (as defined in Section 2.1.2.1) will be summarized by visit using descriptive statistics. Further details on the handling of laboratory parameters are described in Section 2.1.3.

• Immunogenicity Assessments

A serum sample is defined as anti-drug antibody (ADA)-positive if results of the antiglepaglutide antibody screening and confirmatory assays are positive. If positive, a titer (highest dilution factor that still yields a positive reading) will be reported. Patients without any ADA data (evaluable samples) will be excluded from the analysis.

- 1. Pre-existing ADA (Yes/No) is defined, at the patient level, by the ADA status at trial baseline (i.e. Day 4 of MBS at V1), according to the presence or absence of ADA. This will be missing for patients without a valid ADA assessment at baseline.
- 2. A treatment-boosted ADA positive patient (Yes/No) is defined, at the patient level, by an at least 4 fold increase from trial baseline in ADA-titer at any visit for patients with pre-existing ADA (and a titer at baseline). Thus, it will be missing, if pre-existing ADA is missing or no post-baseline sample is available. It will be "Yes", if the sample at any visit shows a 4 fold increase from baseline and "No" otherwise.

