Analysis of ADA positive patients by visit will be done separately and combined, for patients with and without pre-existing ADA. For patients with pre-existing ADA, 'treatment-boosted ADA by sample' is defined as a post-baseline ADA positive sample at a given visit with a titer that has increased at least 4-fold from baseline. For patients without pre-existing ADA, 'treatment-induced ADA by sample' is defined as a post-baseline ADA positive sample at a given visit. For all patients, "ADA positive by sample" is defined as either treatment-boosted by sample or treatment-induced by sample.

The overall anti-glepaglutide antibody incidences (all ADA positive patients) will be presented.

The percentage of "ADA positive by sample" patients will be summarized by visit.

Similar tables will be made separately for "treatment boosted ADA by sample" and "treatment induced ADA by sample", if both types are observed.

For all treatment induced ADA positive patients, the titer levels will be summarized by visit using descriptive statistics including median, geometric mean, geometric CV%, inter-quartile range, minimum, maximum, and number of observations (positive samples only).

For all treatment boosted ADA positive patients (if applicable), the titer levels and fold increases from baseline of titers will be summarized by visit using descriptive statistics including median, geometric mean, geometric CV%, inter-quartile range, minimum, maximum, and number of observations (positive samples only).

All immunogenicity data will be listed, including corresponding PK concentrations.

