3-6.5.1- 3-6.5.4	Titer levels of treatment induced ADA positive patients by visit - Anti-glepaglutide antibodies (ADA) - Reactivity to M2 - Cross-reactivity to glucagon-like peptide [GLP]-2 - Glepaglutide neutralizing antibodies (NAb) Note: Only treatment induced ADA positive patients	SAS

No.	Title/Content	Analysis Sets
3-6.6.1- 3-6.6.4	Titer levels of treatment boosted ADA positive patients by visit - Anti-glepaglutide antibodies (ADA) - Reactivity to M2 - Cross-reactivity to glucagon-like peptide [GLP]-2 - Glepaglutide neutralizing antibodies (NAb) Note: Only treatment boosted ADA positive patients	SAS
3-6.7.1- 3-6.7.4	Fold increase [%] in titer levels of treatment boosted ADA positive patients from baseline by visit - Anti-glepaglutide antibodies (ADA) - Reactivity to M2 - Cross-reactivity to glucagon-like peptide [GLP]-2 - Glepaglutide neutralizing antibodies (NAb) Note: Only treatment boosted ADA positive patients	SAS

List of Data Listings

Analysis Sets:

ALL = All Patients Included into the Trial

ENR = Enrolled Patients

No.	Title	Set	Variables to be included/Variables of the following form in the eCRF and corresponding derived variables
Patient	Disposition and Baseline Charact	eristics	
1-1	Patient disposition - Allocation to analysis sets, reasons for exclusion from analysis sets	ALL	Date of birth, Screening date; Informed consent date; Rescreenings; FAS, PPS, SAF; exclusion from FAS, PPS, SAF;
1-2	Inclusion and exclusion criteria	ALL	Eligibility check variables (Dosing Criteria – Eligibility and Inclusion/Exclusion Criteria forms)
1-3.1	Study completion	ENR	Completion of treatment phase; Reasons for premature discontinuation (Treatment Completion Status form); Compliance with time window for Week 52 (EOT)
1-3.2	Completion of full study	ENR	Completion of full study; Reason for non-completion (Trial Completion Status form)
1-4.1	Study duration	ENR	Last Visit during treatment phase; Withdrawal Date; Follow-up visit performed
1-4.2	Treatment duration	ENR	First and last trial product administration; Duration of trial product administration; Drug exposure;
1-5	Visit dates	ENR	Visit; Visit Date incl. unscheduled visits and corresponding reason (Date of Visit form)
1-6.1	Protocol deviations - overall	ENR	Data from protocol deviations log

No.	Title	Set	Variables to be included/Variables of the following form in the eCRF and corresponding derived variables

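### The SAP defines fold increase as percent change, a scale on which the planned geometric summary of titer rises is undefined or misleading and the 4-fold boosting rule has two readings.

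*SAP*

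**What the plan says.** Four places in the SAP bear on this.

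- **Section 2.1.2.1 (definition).** "The relative change (fold increase) [%] is calculated by dividing the absolute change by the baseline value". The result is then scaled to percent. I find no other definition of fold increase in the SAP. The only outputs that use a relative change are those for antibody titers.
- **Section 4.4 (boosting rule).** At patient level, treatment-boosted status is defined "by an at least 4 fold increase from trial baseline in ADA-titer at any visit for patients with pre-existing ADA". At sample level, the rule is a positive post-baseline sample "with a titer that has increased at least 4-fold from baseline". Section 5 repeats the patient-level rule for the interim analysis. Section 4.4 also carries the definitions over to neutralizing antibodies, M2 reactivity and GLP-2 cross-reactivity.
- **Section 4.4 (summary).** For treatment-boosted patients, "the titer levels and fold increases from baseline of titers will be summarized by visit using descriptive statistics including median, geometric mean, geometric CV" and further statistics, using positive samples only.
- **Appendices.** Tables 3-6.7.1 to 3-6.7.4 are titled "Fold increase [%] in titer levels of treatment boosted ADA positive patients from baseline by visit". Listing 3-17.5 and the interim versions of the tables in Appendix D carry the same percent label.

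**The concern.** There are two separate problems.

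The first is the summary statistic. A geometric mean suits ratios of titers, which are always positive. The quantity that Section 2.1.2.1 calls fold increase is the ratio minus one, times 100, and it can be zero or negative. The SAP has no rule for such values in a geometric mean, so a programmer would have to improvise one.

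The second is the classification. The boosting rule uses the same term that Section 2.1.2.1 ties to percent change. If the definition is carried into the rule, the cut-off is not the one that most readers would assume. Boosted status feeds the definition of an ADA-positive patient and so the overall antibody incidence in Table 3-6.1. Immunogenicity is a listed safety endpoint in both documents.

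**Working it through.** **Inputs.** The formula comes from SAP 2.1.2.1, and the threshold of 4 from SAP 4.4 and 5. A titer is the highest dilution factor that still reads positive (SAP 4.4), so it is always above 0. The documents do not give the dilution step. The plan reports no computed figure here that could be reproduced; the 4-fold threshold is a chosen rule.

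**Step 1: the SAP formula in terms of the ratio.** With baseline titer B, visit titer V and ratio r = V/B, the SAP's fold increase is (V − B)/B × 100 = (r − 1) × 100.

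| Ratio r | SAP fold increase | r ≥ 4? | At least 400%? |
|---|---|---|---|
| 0.5 | −50% | no | no |
| 1 | 0% | no | no |
| 2 | 100% | no | no |
| 4 | 300% | yes | no |
| 5 | 400% | yes | yes |
| 8 | 700% | yes | yes |

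**Step 2: the geometric mean.** It is exp(mean of log x), so every x must be above 0. Three illustrative sets of ratios at one visit:

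| Ratios | SAP percentages | Geometric mean of percentages | Geometric mean of ratios |
|---|---|---|---|
| 4, 8, 16 | 300, 700, 1500 | (300 × 700 × 1500)^(1/3) = 680 | 512^(1/3) = 8.0, i.e. 700% |
| 4, 8, 1 | 300, 700, 0 | needs log 0: undefined, or collapses to 0 | 32^(1/3) = 3.17 |
| 4, 8, 0.5 | 300, 700, −50 | log of a negative number: undefined | 16^(1/3) = 2.52 |

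The geometric CV rests on the same logarithms and fails in the same cases. The ratio gives a usable value in all three.

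**Step 3: can a titer at or below baseline enter the table?** Yes. Boosted status is set once per patient, from any visit. The table is by visit and takes every positive sample from boosted patients. A patient who first meets the rule at Week 24 but was still at the baseline titer at Week 4 contributes a 0 to the Week 4 row.

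**Step 4: the two readings of the boosting rule.** Read as a ratio, the cut-off is r ≥ 4. Read through Section 2.1.2.1 as 400%, it is (r − 1) × 100 ≥ 400, so r ≥ 5. Because any visit can qualify a patient, patient-level status differs only when the highest post-baseline ratio satisfies 4 ≤ r < 5.

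How often that happens depends on the dilution step, which has to be assumed:

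- With 2-fold steps the possible ratios are 1, 2, 4, 8. A ratio of 4 falls in the gap, and the 400% reading is first met at 8.
- With 4-fold steps (1, 4, 16), a ratio of 4 again falls in the gap.
- With 3-fold steps (1, 3, 9) or 5-fold steps (1, 5, 25), no ratio falls in the gap and the readings agree.

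**The case against.** The boosting rule stands on its own. It is written three times without a percent sign and never refers to Section 2.1.2.1, although the SAP cites that section elsewhere when it wants its formula. The sample-level wording, "with a titer that has increased at least 4-fold from baseline", is ordinarily a ratio of 4. To reach a ratio of 5, a reader must import the percent formula and also rescale the threshold to 400%. This stands. A reader might infer that the plan's 4-fold rule is in fact a 5-fold rule, but the documents support only an ambiguity, with the ratio of 4 as the natural reading.

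A reader might also infer that the planned geometric means cannot be computed at all. The documents do not support that. Geometric means of titer levels (Tables 3-6.5 and 3-6.6) are unaffected. Negative samples are kept out of the fold-increase summary, so the value set for them for illustration does no harm. The logarithm fails only at visits where an included positive titer is at or below baseline. Median, quartiles, minimum and maximum are valid throughout, and SAP 4.1 limits geometric statistics to where they apply. However, Section 4.4 specifically calls for them here, and where the percent version exists it is still not the geometric mean fold rise.

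The consequence is also limited. Immunogenicity is summarized descriptively with no test attached, and titers are listed by visit (Listing 3-17.4), so any classification can be rebuilt. This also stands.

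**Conclusion.** The point holds as a defect in a stated calculation, with narrow reach. The percent definition is wrong for the geometric summary in Tables 3-6.7.1 to 3-6.7.4: undefined at some visits and not a geometric mean fold rise at the others. Separately, the shared term leaves the boosting cut-off open to two readings, which differ only for peak ratios from 4 to below 5.

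Whichever reading is meant, text and output do not match. If the cut-off is a ratio of 4, a patient who just qualifies by a 4-fold rise appears in the table with a fold increase of 300%.

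The size cannot be given as an expected number of patients, because the documents state neither the frequency of pre-existing reactivity nor the dilution step. One reclassified patient among the 10 planned in protocol Section 9.2 moves incidence by 10 percentage points if all 10 are evaluable. Across the enrollment range of 6 to 16 in protocol Section 4.1, it is 1/6 = 16.7 to 1/16 = 6.3 points.

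If no patient has pre-existing reactivity, no result changes. Treatment-induced status does not use the rule. The primary and key secondary analyses use absolute change and are unaffected.

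**What to change.** 1. In SAP 2.1.2.1, keep percent change as its own term. For titers, define fold increase as visit titer divided by baseline titer, with no percent.
2. In Section 4.4 (patient-level and sample-level rules) and Section 5 (interim rule), state the boosting cut-off as a ratio of 4 or more.
3. In Section 4.4, specify geometric mean and geometric CV of that ratio.
4. Remove the percent label from Tables 3-6.7.1 to 3-6.7.4 in Appendix A, their interim versions in Appendix D, and Listing 3-17.5 in Appendix B.

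The cost is wording and label edits plus one derivation in the programs. No new data are needed. The change should be made before database lock, so that the cut-off is fixed before anyone can see whom it affects.

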2.1.2.2 Change from Visit x to Visit y

The absolute change from Visit x to a certain Visit y after Visit x will be calculated as the value at the Visit y minus the value at Visit x. If any of the two values is missing, the absolute change from Visit x to Visit y will be missing.

2.1.3 Safety Laboratory parameters: Values reported as '< x' or '> x'

Values reported as '< x' or '> x' will be set to 'x' for quantitative analyses (e.g. for the calculation of mean values in summary tables and for the calculation of changes between visits). This means that values below the lower limit of quantification will be set to the lower limit of quantification for quantitative analyses.

2.2 Primary Endpoint

The primary objective of this study, which investigates the effect on intestinal absorption, is to demonstrate the 24-week effect of glepaglutide on the absorption of fluids. Therefore, the primary endpoint is change from baseline to Week 24 in absorption of wet weight/fluids assessed by 48-hour MBS.

2.2.1 Metabolic Balance Study

An 48-hour MBS will be conducted at baseline (V1) and at V9. The start of the 48-hour sample collection should be on Day 2 of the MBS in the morning, collection continues throughout Day 3 of the MBS and ends on Day 4 of the MBS in the morning.

Several efficacy parameters of the MBS are collected separately for the first and second 24-hour period:

- oral wet weight intake [solid and fluid]
- wet weight output [fecal and urinary]
- energy intake and output
- intake and fecal output of macronutrients
- intake and fecal output of electrolytes and
- urinary excretion of electrolytes.

Data for the first 24-hour period are documented in the eCRF at Day 2 (MBS) and data for the second 24-hour period are documented in the eCRF at Day 3 (MBS). To obtain per day measures for these parameters, values of the first and second 24-hour period will be averaged.

Thus, the following formula is used to obtain an average per day measure at baseline:

Efficacy data item (unit/d) =

{Efficacy data item (unit/d) [Visit 1 – Week 0 – Day 2 (MBS)] + Efficacy data item (unit/d) [Visit 1 – Week 0 – Day 3 (MBS)]} / 2

In case one of the measures assessed for the first or second 24-hour period (Day 2 or Day 3 in the eCRF) is missing, the per day measure is obtained as follows:

For patients without parenteral support (PS):

If at least one of the two 24-hour measurements from the assessments of the 48-hour MBS period is recorded, the assessment will be used in the analysis.

For patients with PS:

As data recorded during one of the 24-hour period (on PS) is not representative for the other 24-hour period (off PS), both assessments need to be available to use the average of these values for analysis.

In case both 24-hour measuresments are missing, the respective average per day measure is also missing.

Analogously, the efficacy data items for Week 24 are calculated based on the information in the eCRF at Visit 9 – Week 24 – Day 2 (MBS) and Visit 9 – Week 24 – Day 3 (MBS).

2.2.2 Fixed fluid intake and 48-hour urine volume

The oral liquid intake should be kept constant, i.e. the fixed drinking menu should be followed during the following time periods:

- During the 48-hour of MBS (at V1 and V9)
- During the 48-hour pre-visit urine collection periods (prior to V2 -V8).

After V9 (i.e. V10 to V12 and Follow-Up Visit), patients should record their fluid intake during the 48-hours pre-visit urine collection periods, which is not restricted to the fixed drinking menu any more.

In the eCRF, the total drinking volume (mL) (equal to total oral liquid intake in fixed drinking menu or deviating total oral intake) during the 48-hour MBS at V1 and V9 and during the

48-hour pre-visit urine collection periods prior to V2 to V8, V10 to V12 and the Follow-Up Visit is documented.

Urine volume will be recorded in the diary during the defined 48-hour measurement periods prior to a trial visit. Additionally, total urine volume (mL) is recorded during the 48-hour MBS at V1 and V9. Urine volumes (mL) during the first and second 24-hour periods of the 48-hour periods are transcribed to the eCRF and summed to obtain a total 48-hour urine volume.

2.2.3 Absorption of Wet Weight/Fluids

Absorption of wet weight/fluids is calculated as oral intake (liquid and solid) minus fecal output, thus:

Absorption of wet weight/fluids (g/d) = Wet weight intake: oral fluid (g/d) + Wet weight intake: oral solid food (g/d) – Wet weight output: Feces (g/d)

The values of the following efficacy data items will be calculated as described in Section 2.2.1:

- Oral wet weight intake (liquid) (g/d) [collected in eCRF as 'wet weight intake: oral fluid (g/d)']
- Oral wet weight intake (solid) (g/d) [collected in eCRF as 'wet weight intake: oral solid food (g/d)']
- Fecal wet weight output (g/d) [collected in eCRF as 'wet weight output: Feces (g/d)']

Absorption of wet weight/fluids (g/d) will be analyzed at baseline and Week 24. Change from baseline to Week 24 for absorption of wet weight/fluids (g/d) is calculated as described in Section 2.1.2. and will be analyzed at Week 24.

The primary analysis will be based on observed data, missing data will not be replaced.

2.3 Secondary Endpoints

Secondary objectives of this study are:

- To assess the effects of glepaglutide on absorption of energy, absorption of the individual macronutrients and absorption of electrolytes
- To evaluate the long-term efficacy of glepaglutide in patients with SBS
- To describe the long-term safety of glepaglutide.

These objectives are operationalized by the following secondary endpoints:

2.3.1 Key secondary endpoint

The key secondary endpoint is change from baseline to Week 24 in absorption of energy (oral intake minus fecal excretion) measured by 48-hour metabolic balance studies. Energy absorption is measured by bomb calorimetry.

Absorption of energy during the MBS at V1 and V9 is measured as oral intake (liquid and solid) minus fecal output and thus calculated as

Absorption of energy (kj/d) = Energy metabolism: energy intake (kj/d) – Energy metabolism: energy output (kj/d)

The calculation of the following items

- Energy metabolism: energy intake (kj/d)
- Energy metabolism: energy output (kj/d)

is done as described in Section 2.2.3.

Absorption of Energy (kj/d) will be analyzed at Baseline and Week 24. Change from baseline to Week 24 for Absorption of energy (kj/d) is calculated as described in Section 2.1.2 and will be analyzed at Week 24.

Statistical Analysis Plan

2.3.2 Secondary efficacy endpoints

Seondary efficacy endpoints are:

• Absorption of individual macronutrients (carbohydrates, lipids and proteins): Change from baseline to Week 24 measured by 48-hour metabolic balance studies

Absorption of individual macronutrients during the MBS at V1 and V9 is measured as oral intake (liquid and solid) minus fecal output.

Then Absorption of individual macronutrients: Carbohydrates (g/d) is calculated as

Absorption of individual macronutrients: Carbohydrates (g/d) =

Macronutrients: Carbohydrate intake (g/d) - Macronutrients: Carbohydrate fecal output (g/d)

The calculation of the following items

- Macronutrients: Carbohydrate intake (g/d)
- Macronutrients: Carbohydrate fecal output (g/d)

is done as described in Section 2.2.3.

Absorption of individual macronutrients: Carbohydrates (g/d) will be analyzed at Baseline and Week 24. Change from baseline to Week 24 for Absorption of individual macronutrients: Carbohydrates (g/d) is calculated as described in Section 2.1.2 and will be analyzed at Week 24.

Furthermore,

- Absorption of individual macronutrients: Lipids (g/d) [collected in the ecRF as "Fat (g/d)"] and
- Absorption of individual macronutrients: Proteins (g/d) [collected in the eCRF as "Nitrogen (g/d)"]

as well as their changes from baseline to Week 24 are calculated and analyzed analogously to Absorption of individual macronutrients: Carbohydrates (g/d) and its change from baseline to Week 24.

• Absorption of electrolytes (sodium, potassium, calcium and magnesium): Change from baseline to Week 24 measured by 48-hour metabolic balance studies.

Absorption of electrolytes during the MBS at V1 and V9 is measured as oral intake (liquid and solid) minus fecal output.

Then Absorption of Electrolytes: Sodium (mmol/d) is calculated as

Absorption of Electrolytes: Sodium (mmol/d) =

Electrolytes: Sodium intake (mmol/d) - Electrolytes: Sodium fecal output (mmol/d)

The calculation of the following items

- Electrolytes: Sodium intake (mmol/d)
- Electrolytes: Sodium fecal output (mmol/d)

is done as described in Section 2.2.3.

Absorption of Electrolytes: Sodium (mmol/d) will be analyzed at Baseline and Week 24. Change from baseline to Week 24 for Absorption of Electrolytes: Sodium (mmol/d) is calculated as described in Section 2.1.2 and will be analyzed at Week 24.

Furthermore,

- Absorption of electrolytes: Potassium (mmol/d),
- Absorption of electrolytes: Calcium (mmol/d) and
- Absorption of electrolytes: Magnesium (mmol/d)

as well as their changes from baseline to Week 24 are calculated and analyzed analogously to Absorption of Electrolytes: Sodium (mmol/d) and its change from baseline to Week 24.

- For patients with Short Bowel Syndrome with Intestinal Failure (SBS-IF) only:
 - Weekly parenteral support (PS) volume: Change from baseline to Week 12 and 24.

PS volumes (mL) are documented by the patient in the diary and then transcribed to the eCRF page "Diary PS use". Weekly PS volume (mL) at a certain visit is calculated as sum of PS volumes (mL) for all PS bag ids over the seven days of the preceding week (date of visit -1 to date of visit -7) based on the information in the eCRF.

Here the date of visit used at baseline is the date of Visit 1 – Week 0 – Day 4 as documented in the eCRF. At Week 24, the date of Visit 9 – Week 24 – Day 4 is used. Weekly PS volume (mL) will be missing, in case any unknown volume is documented.

In case information on Diary PS use in the week before the baseline visit is available for less than seven days, weekly PS volume (mL) at baseline is determined based on prescribed PS over the seven days before the date of Visit 1 – Week 0 – Day 4. Thus, all PS prescriptions which are valid on date of "Visit 1 – Week 0 – Day 3" are determined. Then, the Weekly PS volume (mL) at baseline is calculated as sum of all weekly volumes (L) for these prescriptions as documented in the eCRF and multiplied by 1000.

Weekly PS volume (mL) will be analyzed at baseline and at Week 12 and 24. The change of weekly PS volume (mL) from baseline to Week 12 and Week 24 is calculated as described in Section 2.1.2 and will be analyzed at Week 12 and Week 24.

 Weekly PS macronutrients (total and individual energy content of carbohydrates, lipids and proteins) and individual electrolytes (sodium, potassium, and magnesium): Change from baseline to Week 12 and 24.

The total weekly PS bag volume (mL) of a certain PS bag administered to a patient in the week preceding a certain visit (date of visit -1 to date of visit -7) is obtained by summing the volume (mL) documented for the corresponding bag identifier on each of the seven days of the week on corresponding "Diary PS use" page in the eCRF. Here the date of visit used at baseline is the date of Visit 1 - Week 0 - Day 4 as documented in the eCRF. At Week 24,

the date of Visit 9 – Week 24 – Day 4 is used. The total weekly PS bag volume (mL) will be missing in case the administered amount was unknown for at least one of the seven days in the time interval used for calculation.

In case information on Diary PS use in the week before the baseline visit is available for less than seven days, the total weekly PS bag volume (mL) of a certain PS bag at baseline is based on the prescription of this PS bag to a patient on date of "Visit 1 – Week 0 – Day 3". It is calculated as the weekly volume (L) for this prescription as documented in the eCRF multiplied by 1000. For each administered (or, in the special case for the baseline visit, prescribed) PS bag in the week preceding a visit, e.g. the weekly carbohydrate (kjoule) intake [based on eCRF information "Macronutrients: Glucose/Dextrose (kjoule/L)" on the "content of PS" page] is calculated as:

(Total weekly PS bag volume (mL) of this PS bag) x [Carbohydrate (kjoule/L) content of this PS bag/1000]

Then this amount is summed over all administered (or, in the special case for the baseline visit, prescribed) PS bags to obtain Weekly PS macronutrients: Carbohydrates (kjoule).

Analogously,

- Weekly PS macronutrients: Lipids (kjoule) [based on eCRF information "Macronutrients: Lipids (kjoule/L)"]
- Weekly PS macronutrients: Proteins (kjoule) [based on eCRF information "Macronutrients: Amino acids (kjoule/L)"

are calculated.

For the weekly content of the following electrolytes the above formula can also be applied with replacement of the unit "kjoule" by "mmol":

- Weekly PS electrolytes: Sodium (mmol) [based on eCRF information "Micronutrients: Sodium (mmol/L)"]
- Weekly PS electrolytes: Potassium (mmol) [based on eCRF information "Micronutrients: Potassium (mmol/L)"]
- Weekly PS electrolytes: Calcium (mmol) [based on eCRF information "Micronutrients: Calcium (mmol/L)"]
- Weekly PS electrolytes: Magnesium (mmol) [based on eCRF information "Micronutrients: Magnesium (mmol/L)"]

Weekly PS macronutrients: Total (kjoule) is calculated as:

Weekly PS macronutrients: Carbohydrates (kjoule) + Weekly PS macronutrients: Lipids (kjoule) + Weekly PS macronutrients: Proteins (kjoule).

Weekly PS macronutrients (total and individual energy content of carbohydrates, lipids and proteins) and electrolytes (sodium, potassium, calcium, and magnesium) will be analyzed at Baseline, Week 12 and Week 24. Changes from baseline to Week 12 and Week 24 are calculated as described in Section 2.1.2 and will be analyzed at Week 12 and Week 24.

